Are investigational drugs, devices, or biologics (test articles) controlled by the Principal Investigator? (See FDA IND and IDE Guidance for information regarding test article control).	 Yes  No If "Yes", describe your plan for control of the test article:	
List any approved drugs, biologics and/or devices being studied:		
G. Other Approvals/Regulated Materials: Does this research involve the use of the regulated materials listed below? If "Yes", additional approvals may be required.		 Yes  No

 - Controlled Substances - Radiation - Human Embryonic Stem Cells – The WHHS IRB cannot approve stem cell research - Fetal Tissue – The WHHS IRB cannot approve research involving fetal tissue 		

PART 2: STUDY DESIGN

Complete items A-E using clear, concise, non-technical, lay language (i.e., the type of language used in a newspaper article for the general public) wherever possible. Define all acronyms.

Space limits are recommendations and should be adjusted as needed, but the total length for sections A-E should not exceed 5 pages.

A. Synopsis (Briefly summarize the research.)	Space limit: quarter page
--	---------------------------

Study Description: This is a randomized prospective study comparing two postoperative leg sleeves. The novel bioactive sleeve (Reparel Leg Sleeve) will be compared to a regular TED stocking. The main hypothesis for this study is that postoperative use of a novel bioactive sleeve after hip replacement will decrease pain and improve patient reported outcome scores faster and more reliably than the control standard TED stocking. In order to test this hypothesis, approximately 50 patients scheduled for hip replacement will be randomized to one of two arms (bioactive sleeve on operative leg and TED stocking on other, versus bioactive sleeve on nonoperative leg and TED stocking on operative leg). The following standard assessment tools will be assessed: patient reported outcomes (VAS, HOOS JR, VR12, and HSS, Satisfaction, Forgotten Joint), study questionnaire. PROMs will fall under chart review activities.

Objectives:

Primary Objective: Assessing the effectiveness of a bioactive sleeve against a non-bioactive TED leg sleeve with regard to pain, swelling, and dvt rates.

Primary Endpoint: Patient reported outcome scores (VAS, HOOS JR, VR12, HSS, Satisfaction, Forgotten Joint).

Secondary Endpoints: Swelling evaluated by routine clinical evaluations. DVT rates monitored.

Study Population: This prospective study hopes to enroll approximately 50 male and female patients over the age of 18 years old and below the age of 90 years old. BMI must be below 40. Subjects volunteer for participation with elective hip replacement.

Description of Study Intervention: This is a device study using a novel bioactive sleeve which is assumed to mimic the effects of photobiomodulation in comparison to a placebo sleeve.

Study Duration: Study duration from when the study opens until the completion of data analysis is expected to be 24 months.

B. Purpose (Specify the hypotheses and/or objectives.)	Space limit: half page
---	------------------------

This prospective study will evaluate pain, swelling, dvt rates as well as narcotic use in post-operative total hip arthroplasty patients using novel non-compressive photobiomodulating stocking (NCPS) versus current standard of care gradient compression stocking (Thrombo-Emolic-Deterrent or TED hose). Disadvantages of standard TED stockings are difficulty of placement, and thereby compliance in the postoperative period. Current literature remains mixed regarding the effectiveness of these stockings in pain, swelling, and dvt reduction. This study will evaluate if NCPS is equivalent, or superior, in these outcome areas, and it may provide a new and comfortable way to reduce patient pain and swelling immediately following hip surgery.

C. Background (Summarize previous research. Explain the rationale for the proposed investigation and if applicable how this research differs from local standard of care.)

Space limit: one page

Total hip arthroplasty (THA) is one of the most common surgical procedures today. It is designed and proven to effectively reduce pain caused by end-stage osteoarthritis. Despite its achievements, post-operative swelling of the hip and leg is thought to be a contributor to pain and delayed rehabilitation.

Traditionally, a standard gradient compression stocking is applied to the leg after surgery to reduce this pain and swelling. However, due to ineffectiveness or patient non-compliance, compression stockings are often not entirely successful at preventing edema. The recently developed NCPS is a lower extremity garment comprised of a technical fabric that is thought to be able to prevent edema and reduce pain all in a comfortable, user-friendly manner. The purpose of this study is to determine if the NCPS is effective at improving post-operative pain, swelling, ROM and analgesic use associated with THA.

Pain and prolonged recovery time associated with post-operative swelling are two factors that contribute to patient dissatisfaction following THA. Swelling of the leg following THA is caused by intraarticular bleeding and inflammation of the periarticular tissues, which can lead to a decrease in functional performance including pain and delayed rehabilitation. Leg swelling can play a part in post-operative quadriceps strength following joint replacement. Ultimately, if post-operative swelling can effectively be reduced, patient recovery could be expedited and patient satisfaction could be improved. Compression stockings have been utilized to attempt to reduce post-operative swelling. Compression works to prevent swelling by reducing the hydrostatic pressure in the leg. Reducing hydrostatic pressure prevents the capillaries from oozing and allows blood to move freely from the superficial to the deep venous system, subsequently allowing excess fluid to flow away from the interstitial space.

More recently, the use of gradient compression stocking following THA has come into question for its efficacy. While the application of external pressure from these gradient compression stocking is beneficial for a period, they are often unable to exert a sufficient amount of pressure long enough to prevent painful edema for an extended amount of time. These garments can show sufficient compression during the first few hours after surgery, but the pressure they applied dropped with time and required daily measurements and refitting to maintain appropriate and therapeutic compression. It's clear that compression stockings are not as effective as once thought when it comes to controlling pain and swelling post-operatively.

A potential solution to the problems posed by traditional compression stocking is the NCPG. The garment is comprised of a semi-conductive material ground to nanoparticles that are embedded into the fibers, formed into a three-dimensional woven fabric for optimized comfort. Instead of relying on compression, NCPS utilizes the body's own thermal energy to generate infrared energy. The infrared energy generated is reflected back at the body and modifies cellular activity at the level of the mitochondria through a process known as photobiomodulation. This process of photobiomodulation is hypothesized to improve swelling and tissue healing by increasing the activity of mitochondria and the availability of cellular energy in the form of ATP.

WASHINGTON HOSPITAL HEALTHCARE SYSTEM
INSTITUTIONAL REVIEW BOARD

D. Design	
1. (Check all that apply):	
[x] Phase I [] Phase II [] Phase III [] Phase IV [x] Randomized [] Blinded	
[] Behavioral [] Interventional	
[] Multicenter: If so, is Washington Hospital the coordinating center or the primary grant holder?	[] Yes [] No
2. Additional description of general study design . Attach flow diagram if appropriate. Space limit: half page	
Inclusion Criteria	
1. Age range: from 18 to 89	
2. Primary unilateral Total Hip Replacement	
Exclusion Criteria	
1. Physical condition prohibiting use of leg stocking or garment	
2. Allergy to silicone/polyester	
4. Current DVT	
5. History of Vascular Bypass Surgery on Operative Limb ie) Fem-Pop or Fem-Fem	
6. Inability to follow standardized post op and rehab protocols	
7. Lymphedema	
Number of Research Participants	
We will enroll 50 subjects throughout all sites involved in the study.	
E. Data Analysis (How and by whom will data be analyzed?) Space limit: half page	
PI and reparel sponsor will analyze subject questionnaires using statistical data analysis using the results provided by each subject and the PI. Study team will evaluate each criterion and analyze the results of each subject. Routine clinical evaluations will be summarized. The information will be statistically summarized using the criteria identified above and measuring based upon the subject's questionnaires	

WASHINGTON HOSPITAL HEALTHCARE SYSTEM
INSTITUTIONAL REVIEW BOARD

PART 3: PROCEDURES


A. List, in sequence, all research procedures, tests and treatments required for the research. Indicate which would be done even if a subject does not enroll in the research. Include a detailed explanation of any experimental procedures. Attach table if available.
 
1. PI will identify 50 subject candidates willing to participate in the study. 2. Subjects randomized to bioactive sleeve on one leg and TED stocking on other. 3. Routine clinical evaluations performed 4. Patient questionnaires completed 5. Questionnaires and data analyzed, summarized and results presented
	

B. List the specific locations where research procedures will be performed. Indicate how much time will be required of the subjects, per visit and in total for the research.
 
1. PI offices: [name] Orthopedics 2. Normal routine clinical followup, up to 5 minutes for questionnaires
	

C. Will any interviews, questionnaires, surveys or focus groups be conducted for the research? If "Yes," please list any standard instruments used for this research and attach any non-standard instruments. Note: All non-standard instruments must be approved by the WHHS IRB prior to use.
 
Interviews, questionnaires, surveys will be conducted for the research using oral and online communication. Standard instruments: Hoos Jr, Pain Score, Patient Questionnaire, Global 7, Forgotten Joint Score Attached forms: Reparel Patient Questionnaire
	 Yes  No

D. Will subjects or their health care provider be given the results of any experimental tests that are performed for the research? If "Yes" please describe the tests, provide a rationale for providing subjects with the experimental test results and explain what, how and by whom, subjects and their health care provider will be told about the meaning, reliability, and applicability of the test results for health care decisions.
	 Yes  No

WASHINGTON HOSPITAL HEALTHCARE SYSTEM
INSTITUTIONAL REVIEW BOARD

PART 4: ALTERNATIVES

A. Describe the alternatives to research participation that are available to prospective subjects.	
No participation nor research	
B. Is study drug or treatment available off-study? If "Yes", discuss this in the consent form.	 Yes  No  N/A

PART 5: RISKS AND BENEFITS

A. Risks and Discomforts 1. Describe the risks and discomforts of any investigational or approved drugs, devices and procedures being used or assigned for research purposes. Describe the expected frequency of particular side effects. If subjects are restricted from receiving standard therapies during the research, also describe the risks of those restrictions.
No expected discomforts from using bioactive sleeve garment compared to traditional TED stocking. Study to assess amount of leg swelling, discomfort, dvt rate versus traditional stockings. TED stocking will be used on either operative or non-operative leg in all cases. Literature suggests this alone has an anti-dvt effect. Therefore, expected risks rare and minimal.
2. Describe the steps taken to minimize the risks/discomforts to subjects (e.g., supportive interventions or special monitoring):
Patients have clinic support and staff availability as standard of care
B. Data and Safety Monitoring Plan (DSMP): All interventional studies involving more than minimal risk must include a DSMP. A DSMP is a plan established to assure that each research study has a system appropriate oversight and monitoring of the conduct of the research to ensure the safety of participants and the validity and integrity of the data. Note: Most, but not all studies (i.e., non-interventional studies) undergoing WHHS IRB review will require a DSMP.

WASHINGTON HOSPITAL HEALTHCARE SYSTEM
INSTITUTIONAL REVIEW BOARD

This is an interventional study and thus does require a DSMP [] Yes
Describe the DSMP Plan: Patients will be evaluated with routine postoperative phone calls at intervals within 1 week, 2 week, 4 weeks. In addition, clinical evaluations will occur at 2 week, 6 week, 12 weeks. Safety will be evaluated at each of the above mentioned followups. PI will assess all data and clinical evaluations. Monthly and quarterly review of research conduct will be reviewed by PI to assure safety of study, and validity/integrity of data.
This is a non-interventional study and thus does not require a DSMP. [] Yes
C. Adequacy of Resources: Principal Investigators must have the necessary resources required to conduct the proposed research in a way that assures the rights and welfare of participants are adequately protected. Depending on the nature of the research study, investigators should consider the proximity or availability of critical resources that may be essential to the safety and welfare of participants. For example, the proximity of an emergency facility for care of participant injury, or availability of psychological support after participation, or resources for participant communication, such as language translation services. Please describe below the resources you have in place to conduct this research in a way that assures protection of the rights and welfare of participants. This includes having adequately trained research staff and data systems to support the study:
This is a non-interventional study and thus does not require a DSMP. [] Yes Standard postoperative care and followup are provided for study patients as for our standard non-study patients. These resources are adequate and appropriate to assure protection of rights and welfare of participants. Study performed by staff trained and educated to perform research.
D. Confidentiality and Privacy: Privacy concerns people, whereas confidentiality concerns data. Specifically, confidentiality refers to the researcher's plan to handle, manage and disseminate the participant's identifiable private information. Privacy refers to a person's wish to control the access of others to themselves. Address each of the following privacy issues questions 1-3 below:
1. How will the investigator access information from or about participants? This is a non-interventional study and thus does not require a DSMP. [] Yes Information will be same information used for non-study patients with standard postoperative care. EMR will be used as routine for joint replacement patients.
2. How will the investigator maintain privacy in the research setting(s)? All data will be in the privacy of the subject's home or office clinic. Confidentiality of participants Protected Health Information (PHI) will be protected through locked cabinets for participant records containing PHI. Investigators will utilize password protected programs and access to PHI will be limited to investigators only. Data collected from questionnaires and during testing will be stored in a locked cabinet that is accessible only to study personnel. Participants will not be identifiable by name or description in publications of this study.
3. What are the consequences to participants of a loss of privacy (e.g., risks to reputation, insurability, and other social risks)?

WASHINGTON HOSPITAL HEALTHCARE SYSTEM
INSTITUTIONAL REVIEW BOARD

No additional data or information collected that is not standard. Therefore, same risks of privacy loss as with any EMR system.
		

The following questions address confidentiality issues:
		

4. Identifiers: Please indicate all identifiers that may be included in the research records for the study. Check all that apply.
		
 Names  Dates  Address  Phone numbers  Fax numbers  Email address	 Social Security numbers  Medical records numbers  Health plan numbers  Account numbers  License/Certificate numbers  Vehicle id numbers	 Device identifiers/Serial numbers  Web URLs  IP address numbers  Biometric identifiers  Facial Photos/Images  Any other unique identifier  None of the 18 identifiers listed above

5. Determining Whether HIPAA Regulations Apply to This Research: Please answer the questions below for the identifiers marked in the above section. Check all that apply:
		

Are research data:
 
 Derived from a medical record?  Added to the hospital or clinical medical record?  Created or collected as part of health care?  Used to make health care decisions?
	
HIPAA regulations apply.
	

 Obtained from the subject, including interviews, questionnaires?  Obtained from a foreign country or countries only?  Obtained from existing research records?
	
HIPAA regulations do not apply.
	

If HIPAA regulations apply, you are required to obtain individual subject authorization or a waiver of authorization. This authorization requires a separate signature by the research subject.
		

6. Use and Disclosure of Protected Health Information: Please indicate to whom or where you may disclose any of the identifiers listed above as part of the study process. Check all that apply:
 
 The subject's medical record.  The study sponsor: please indicate: Reparel  The US Food & Drug administration (FDA)  Others: please indicate: IRB  A Foreign County or Countries  We do not plan to share any of the PHI listed above outside the research team.
		

7. Data Security: Identifiable data should not be stored on laptops, PDA's or other portable devices. Please indicate how study data are kept secure Check all that apply:
 
 Data are coded; data key is destroyed at end of study or provide date: _____  Data are coded; data key is kept separately and securely  Data are kept in locked file cabinet  Data are kept in locked office or suite  Electronic data are protected with a password  Data are stored on a secure network
		

8. Describe any additional steps taken to assure that identities of subjects and any of their health information which is protected under the law is kept confidential. If video or audio recordings will be made as part of the research, disposition of these recordings should be addressed here and in the consent form.
		

WASHINGTON HOSPITAL HEALTHCARE SYSTEM
INSTITUTIONAL REVIEW BOARD

NA	
9. Reportable Information: Is it reasonable and/or foreseeable that the study will collect information that state or federal law requires to be reported to other officials (e.g., child or elder abuse) or ethically requires action (e.g., suicidal ideation)? If "Yes," please explain below and include a discussion of the reporting requirements in the consent form.	 Yes  No

E. Benefits:
 
1. Are there potential direct benefits to research subjects? If "Yes," please describe below.
 
It is hoped that subjects...
 
 - Less pain, less swelling, comparable or lower dvt rates 
2. What are the potential benefits to society?
 
Faster and more comfortable recovery after hip replacement surgery
	

F. Risk/Benefit Analysis: How do the benefits of the research outweigh the risks to subjects?
 
No risks or adverse events are anticipated as a result of the tests. There is minimal risk to the subject and maximum gains in improved strength, health and wellbeing.
	

PART 6: SUBJECT INFORMATION

A. Number of Subjects:	
1. How many subjects will be enrolled at WHHS and affiliated institutions?	50
2. How many subjects will be enrolled at all sites (i.e., if multicenter research)?	0
3. How many people do you estimate you will need to consent and screen here (but not necessarily enroll) to get the needed subjects?	70
B. Types of Subjects: Check all that apply.	
	Children – Complete Part 6.H of the Application
	Subjects Unable to Consent
	Subjects with Diminished Capacity to Consent
	Subjects Unable to Read, Speak, or Understand English – Complete Part 8.D of this application
	Pregnant Women – Complete Part 6.G of this application
	Fetuses – Complete Part 6.G of this application

WASHINGTON HOSPITAL HEALTHCARE SYSTEM
INSTITUTIONAL REVIEW BOARD

	Neonates – Complete Part 6.G of this application
	Prisoners
	Inpatients
	Outpatients
	Healthy Volunteers
	Staff of WHHS or WHHS affiliated institutions,
	Students of WHHS
C. Eligibility Criteria:	
1. General description of subject population(s): Elective hip replacement patients.	
2. Inclusion Criteria: 50 subjects age 18-89 years of age. 50% male and 50% female All subjects will have comparable levels of joint arthritis that present imminent surgical options or may present future surgical options. All subjects will be selected by the PI	
3. Exclusion Criteria: Subjects <18 or >90 years of age Subjects determined to be of high risk to participate by PI 1. Physical condition prohibiting use of leg stocking or garment 2. Allergy to silicone/polyester 4. Current DVT 5. History of Vascular Bypass Surgery on Operative Limb ie) Fem-Pop or Fem-Fem 6. Inability to follow standardized post op and rehab protocols 7. Lymphedema	
D. Determination of Eligibility: How (chart review, additional tests/exams for research purposes), when and by whom will eligibility be determined? Subjects will be screened initially by PI/team, for eligibility Consent obtained after participation confirmed. Bioactive sleeve garment and TED stocking supplied at time of surgery Routine clinical followup and questionnaires provided	
E. Are there any inclusion or exclusion criteria based on gender, race or ethnicity ? If “Yes,” please explain the nature and rational for the restrictions below.	
na	

WASHINGTON HOSPITAL HEALTHCARE SYSTEM
INSTITUTIONAL REVIEW BOARD

F. Populations Likely to be Vulnerable to Coercion or Undue Influence: List subject groups who are likely to be vulnerable to coercion or undue influence, such as mentally disabled persons, economically or educationally disadvantaged persons, or investigators' staff or students. For pregnant women, fetuses and neonates, see section 6.G Below: Note: For other vulnerable groups, separate, specific regulations may apply.
na
2. Explain why it is appropriate to include the groups listed above in this particular research:
na
3. Describe additional safeguards that have been included in the research to protect the rights and welfare of these subjects and minimize coercion or undue influence. For example, you might provide competence evaluations (specify) for the mentally disabled, payment amounts calibrated to be non-coercive for the financially disadvantaged, extra-careful evaluations of subjects' understanding of the research, advocates to be involved in the consent process, or use flyers to recruit subjects instead of directly approaching staff or students:
NA
G. Pregnant Women, Human Fetuses and Neonates: Identify all sections of 45 CFR 46 Subpart B under which you believe the research falls and provide study-specific information showing why the research falls within those sections:
na
H. Children Identify all sections of 45 CFR 46 Subpart D under which you believe the research falls and provide study-specific information showing why the research falls within those sections:
na

PART 7: RECRUITMENT

A. Any advertisements, whether posted or broadcast, and all correspondence used for purposes of recruitment require IRB review and approval before they are used. Check all that apply:
 Research investigators recruit their own patients directly and/or nurses or staff working with researcher's approach patients. Please explain in Section B below.
 Research investigators send an IRB approved letter to colleagues asking for referrals of eligible patients interested in the research. The investigators may provide the referring physicians an IRB approved Information Sheet about the study to give to the patients. If

WASHINGTON HOSPITAL HEALTHCARE SYSTEM
INSTITUTIONAL REVIEW BOARD

	interested, the patient will contact the PI, or, with documented permission from the patient, the PI may be allowed to talk directly with patients about enrollment. Attach letter for review.
	Research investigators provide their colleagues with a “ Dear Patient ” letter describing the research. This letter can be signed by the treating physicians and would inform the patients how to contact the research investigators. The research investigators may not have access to patient names and addresses for mailing. Attach letter for review.
	Advertisements, notices, and/or media used to recruit subjects. The IRB must first approve the text of these and interested subjects will initiate contact with research investigators. Attach ads, notices or media text for review. In Section B, please explain where ads will be posted.
	Research investigators request a Waiver of Consent/Authorization for recruitment purposes. This waiver is an exception to the policy but may be requested in circumstances such as:
	Minimal risk research in which subjects will not be contacted (i.e., chart review only).
	Review of charts is needed to identify prospective subjects who will then be contacted. (Explain in Waiver form).
	Large-scale epidemiological research and/or other population-based studies when subjects may be contacted by someone other than personal physician. (Explain in Waiver form).
	Direct contact of potential subjects who have previously given consent to be contacted for participation in research. Clinic or program develops an IRB-approved recruitment protocol that asks patients if they agree to be contacted for research (a recruitment database) or consent for future contact was documented using the consent form for another IRB-approved research. Please explain in Section B below.
	Research investigators recruit potential subjects who are unknown to them. Examples include snowball sampling, use of social networks, and direct approach in public situations. Please explain in Section B below.

B. Provide detail in the space below (i.e., how, when, where and by whom are potential subjects approached).
 
PI will select subjects from his subject pool to ensure they are appropriate for the study.
	

PART 8: INFORMED CONSENT PROCESS

A. Check all that apply:
 
 Signed consent will be obtained from subjects and/or parents (if subjects are minors).
 
 Signed consent will be obtained from a legally authorized representative.
 
 Informed consent will not be obtained. Complete Waiver of Consent in Section 8.E.
	

B. In the space below, describe how, where, when and by whom informed consent will be obtained. How much time will prospective subjects be given to consider study participation? If special subject populations will be included, be sure to describe any additional plans for obtaining consent from particular populations.
 
PI will discuss the protocol with each subject and provide an Informed Consent form. Subject may additionally contact sponsor to address additional questions.
	

WASHINGTON HOSPITAL HEALTHCARE SYSTEM
INSTITUTIONAL REVIEW BOARD

C. How will you make sure subjects understand the information provided to them?	
Subjects will be provided with oral and written explanations of the protocol and expectation.	
D. Subjects Who Do Not Read, Speak or Understand English.	
1. If you will enroll subjects who are unable to read, speak or understand English, what method will you use to obtain consent? na	
	Preferred Method – Consent form and other study documents will be available in the subject's primary language. Qualified interpreter able to discuss participation in the patient's language will be present, physically or via language line, for the consent process.
	Short-Form – A qualified interpreter will translate the consent form verbally and subjects will be given the Experimental Subject's Bill of Rights and the Short Form Consent in their primary language.
2. How will you maintain the ability to communicate with non-English speakers throughout their participation in the study?	
Study will be focused on English speakers only.	
E. Waiver of Consent:	
A waiver of consent is requested:  Yes  No	
If yes, the investigator certifies that the following criteria are met:	

 • The research involves no more than minimal risk to the subjects. • The research could not practicably be carried out without the requested waiver or alteration. • If the research involves using identifiable private information or identifiable biospecimen, the research could not practicably be carried out without using such information or biospecimen in an identifiable format. • The waiver or alteration will not adversely affect the rights and welfare of the subjects. • Whenever appropriate, the subjects or legally authorized representative will be provided with additional pertinent information after participation. 	

PART 9: FINANCIAL CONSIDERATIONS

A. Payments to Subjects:	
1. Will subjects receive payments or gifts for research participation? If "Yes," complete the following:	
2. Payments will be (check all that apply):  Cash  Check  Other (describe below)	
3. Please describe the schedule and amounts of payments, including the total subjects can receive for completing the research.	
na	

WASHINGTON HOSPITAL HEALTHCARE SYSTEM
INSTITUTIONAL REVIEW BOARD

B. Cost to Subjects: Will subjects or their insurance be charged for any research procedures? If "Yes", describe those costs below and compare subjects' costs to the costs associated with alternative care off-study. Finally, explain why it is appropriate to charge those costs to the subjects.
	
[] Yes  No

C. Treatment and Compensation for Injury: Describe the procedures that will be followed if a subject is injured as a result of participation in the research study.
 
Should the subject feel discomfort while following the oral or written instructions, they should refrain from using the garments and consult with [name]. There is no compensation for injury as injury is not expected.
	

PART 10: BIBLIOGRAPHY

de Freitas, L. F., & Hamblin, M. R. (2016). Proposed mechanisms of photobiomodulation or low-level light therapy. *IEEE Journal of selected topics in quantum electronics*, 22(3), 348-364.

Brennecka, G.L. (2016). Optical Response of Reparel Fabrics, 0.3 – 2.5 μm . Colorado School of Mines.

PART 11: ATTACHMENTS

WASHINGTON HOSPITAL HEALTHCARE SYSTEM
INSTITUTIONAL REVIEW BOARD

Please list Attachments, Supplements and Appendices Indicate with an asterisk (*) any document that requires IRB approval.	Version number(s) or date(s)

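### DVT is to be judged equivalent or superior, but it is only monitored through routine, unblinded care, with no confirming test, time window or leg to count, so unequal testing between arms could neither be ruled out nor seen

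*Protocol*

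**What the plan says.** - **Weight of DVT.** The primary objective (Part 2.A) is "Assessing the effectiveness of a bioactive sleeve against a non-bioactive TED leg sleeve with regard to pain, swelling, and dvt rates". The Purpose (Part 2.B) adds the comparative aim: "This study will evaluate if NCPS is equivalent, or superior, in these outcome areas". No margin is attached.
- **Ascertainment.** The secondary endpoints (Part 2.A) give the whole definition: "Swelling evaluated by routine clinical evaluations. DVT rates monitored".
- **Procedures.** The list in Part 3.A has no DVT test. After randomisation it reads "3. Routine clinical evaluations performed 4. Patient questionnaires completed", followed by analysis.
- **Contacts.** Part 5.B states "Patients will be evaluated with routine postoperative phone calls at intervals within 1 week, 2 week, 4 weeks", plus clinic evaluations at 2, 6 and 12 weeks, with safety looked at each time and the investigator assessing all data. The schedule is the same in both arms.
- **Data source.** Part 5.D.1 says the information is that used for non-study patients and names the EMR. Part 5.D.3 says "No additional data or information collected that is not standard".
- **Blinding.** The design boxes (Part 2.D) read "x] Randomized [] Blinded", with the second box empty.
- **Garments.** Each patient wears the sleeve on one leg and the TED stocking on the other. The arms differ in which garment is on the operative leg (Part 2.A).

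**The concern.** Without a scheduled test, a DVT enters the data only if someone suspects it and looks. Two features of this trial could make that looking unequal.

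First, the sleeve is expected to reduce pain and swelling. If those symptoms help to raise suspicion of a clot, which is a reasonable clinical inference but not something the protocol states, fewer patients with the sleeve on the operative leg might be tested. Second, the team knows which operative leg has the non-compressive garment, and Part 5.A tells them that the literature credits the TED stocking with protection against DVT. That could lead to more testing in the sleeve-on-operative-leg arm.

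The two influences oppose each other. Randomisation does not protect against differences in detection that arise after allocation, and an equal contact schedule equalises the chances to look, not the decisions to look.

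The unspecified leg adds a separate difficulty. Because every patient wears both garments, a patient-level DVT count does not say which garment the affected leg was wearing.

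At stake is the reading of any DVT difference. A lower rate could reflect less testing and a higher one more suspicion, and a safety signal for a garment that replaces compression on the operative leg could be blurred.

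**Working it through.** The protocol gives no DVT rate, margin, power or sample-size derivation, so there is no figure to reproduce. The only numerical input from the document is 50 patients. Twenty-five per arm assumes 1:1 allocation, because no ratio is stated. All rates and detection probabilities below are assumptions.

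**1. Effect of unequal detection.** Observed rate = true rate × probability that a DVT is tested for and found. With equal true rates, observed risk ratio (sleeve on operative leg v TED on operative leg) = ratio of the detection probabilities.

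| Detection, TED v sleeve on operative leg | Observed risk ratio | Expected detected cases per 25, true rate 5% |
|---|---|---|
| 60% v 60% | 1.00 | 0.75 v 0.75 |
| 60% v 40% | 0.40/0.60 = 0.67 | 0.75 v 0.50 |
| 60% v 30% | 0.30/0.60 = 0.50 | 0.75 v 0.38 |
| 40% v 60% | 0.60/0.40 = 1.50 | 0.50 v 0.75 |

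Example: 25 × 0.05 × 0.60 = 0.75. For the 60% v 40% row, the expected counts run from 0.30 v 0.20 at a true rate of 2% to 3.00 v 2.00 at 20%. The ratio does not depend on the true rate.

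**2. Weight of a single event.** 1/25 = 4 percentage points. Two true cases in each arm, with one missed in one arm, would show as 8% v 4%.

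**3. What 25 per arm could show with perfect, equal detection.** Power is the sum of the binomial probabilities of all tables with Fisher p ≤ 0.05 (two-sided). The sample size per arm for 80% power uses the normal approximation for two proportions: n = [1.96·√(2p̄(1−p̄)) + 0.84·√(p₁(1−p₁)+p₂(1−p₂))]² / (p₁−p₂)², where p̄ is the mean of p₁ and p₂.

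| Halving of risk | Power at 25 per arm | n per arm for 80% power |
|---|---|---|
| 2% to 1% | 0.0% | 2319 |
| 5% to 2.5% | 0.1% | 906 |
| 10% to 5% | 1.3% | 435 |
| 20% to 10% | 8.6% | 199 |

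A split of 5 v 0 gives Fisher p = 0.0502. On the equivalence side, even 0 events in 25 leaves a two-sided 95% exact upper limit of 1 − 0.025^(1/25) = 13.7%.

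**4. Can the protocol reveal unequal testing?** Its named sources are routine evaluations, questionnaires and the EMR. None is assigned to record scans ordered, their reason, the leg or the result, by arm.

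**The case against.** The strongest reply has four parts.

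*The mechanism is inferred.* Nothing in the protocol says what prompts a DVT work-up. This stands. A reader might go further and infer that the DVT comparison reflects who is tested as much as who has a clot. The documents cannot support that, because neither the size nor the net direction of any detection difference can be derived from them.

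*Ascertainment is not as bare as it looks.* Safety is considered at three calls and three visits in both arms, the EMR is named, and Part 3.C lists an attached study questionnaire that is not in the document at hand and may ask about clots. The sentence in Part 5.D.3 answers a privacy question and is not an outcome-collection plan. A reader might infer that clots diagnosed elsewhere go uncounted. Nothing says so, and these channels could well pick them up. They still do not supply a definition, a window or a leg, and they do not record testing.

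*The hoped-for result is misread.* A reader might take the comparable or lower DVT rates in Part 5.E as the result that the trial sets out to show. Those words list possible benefits to subjects. The comparative aim is the one in Part 2.B.

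*Sample size defeats the comparison anyway.* DVT is a secondary endpoint and the main hypothesis concerns pain and patient-reported scores. With perfect detection, power to see a halving of risk is still at most 8.6% over the rates examined. This stands too, and it shapes the remedy: better recording cannot rescue an equivalence or superiority claim. It does not excuse loose ascertainment, since with so few events one extra or missed diagnosis can decide how the result looks.

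**Conclusion.** The point holds as a plausible and undetectable source of bias, not as a demonstrated one. DVT carries a comparative claim, but the protocol fixes no confirming test, window or leg for it and relies on routine, unblinded care. Testing could differ between arms in either direction, and no procedure named in the protocol would reveal it.

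The size is unknown. Under the assumed detection probabilities the observed risk ratio runs from 0.50 to 1.50 with no true difference, and one event moves a rate by 4 points if allocation is 1:1. Separately, about 25 patients per arm cannot support an equivalence or superiority conclusion on DVT however well it is ascertained. The finding does not touch the patient-reported outcomes. It should be corrected because DVT is both a stated objective and a safety outcome, and the correction is cheap.

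**What to change.** 1. **Define the event**: imaging-confirmed DVT from surgery to the 12-week visit, recorded by leg and by the garment on that leg, including events diagnosed elsewhere. Make the operative leg the between-arm comparison. Record pulmonary embolism separately as a patient-level safety event, since it cannot be assigned to a leg.
2. **Ask alike**: put one fixed question, covering any leg scan, clot, emergency visit or admission since the last contact, at every call and visit already planned, in both arms.
3. **Make testing visible**: extract from the EMR every leg scan with its reason, leg and result, and report scans by arm beside confirmed events.
4. **Limit the claim**: report DVT descriptively with exact intervals, and remove DVT from the equivalence-or-superiority statement in Part 2.B. Recording scans shows unequal testing but does not remove it.

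The cost is a short script for contacts already scheduled and an EMR extract for 50 patients, with no added imaging. Because this goes slightly beyond standard data, the statement "No additional data or information collected that is not standard" in Part 5.D.3 must be corrected.
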